We will recruit normal weight and obese subjects. For the purpose of this study obesity will be defined as a body mass index (BMI) > 30 kg/m^2 and a waist circumference $\geq 94 \text{ cm}$ for men and $\geq 80 \text{ cm}$ for women. Subjects' post-prandial inflammatory response to a high fat meal and to n-3 fatty acids taken with that meal will be assessed using approaches we have used previously to study acute lipid metabolism and fatty acid appearance in the bloodstream [8,9]. Blood will be taken at several time points during the meal challenge (0, 1, 2, 3, 4 and 6 hours). Each subject will undergo both meal challenges, in random order and separated by at least 2 weeks. Subjects will then be randomised to consume placebo or "fish oil" capsules daily for about 12 weeks. Inflammatory mediators in the bloodstream will be measured at the start and end of this period. Subjects will then repeat the standard meal challenge. A range of inflammatory mediators will be measured in the blood samples. In addition, fatty acid status will be measured in all samples. An adipose tissue biopsy will be taken at study entry and after the 12 week intervention period; this will be used to assess inflammatory cell infiltrate and the levels of genes and proteins involved in inflammation.

Subjects and supplements

Subjects aged 18 to 65 years with normal weight (a body mass index (BMI) between 18.5 and 25 kg/m² (n = 50)) and obesity (BMI 30 to 40 kg/m^2 (n = 50) and a waist circumference $\geq 94 \text{ cm}$ for men and $\geq 80 \text{ cm}$ for women) will be recruited. Subjects will recruited via posters and email shots in the University of Southampton, Southampton General Hospital, and other organisations with which the researchers have contact; and via advertisements in local media including newspapers and radio. Subjects who express an interest will be screened by telephone interview. If they fit the inclusion and exclusion criteria (see below) they will be sent the information sheet. They will be contacted about 7 days later to confirm their interest or not, and if they remain interested an appointment will be made for them to visit the Wellcome Trust Clinical Research Facility at Southampton General Hospital. At this first visit the study will be explained, any questions answered and written consent obtained. Subjects will later make three clinic visits.

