Subjects who express an interest will be screened by telephone interview. If they fit the inclusion and exclusion criteria they will be sent the information sheet. They will be contacted about 7 days later to confirm their interest or not and if they remain interested an appointment will be made for them to visit the Wellcome Trust Clinical Research Facility, Southampton General Hospital. At this first visit the study will be explained, any questions answered and written consent obtained; subjects will then have height, weight, waist and hip circumference, and body composition (bioelectrical impedance) measured to confirm that they meet the inclusion criteria. A 9 ml blood sample will be taken for preparation of DNA. An appointment will be made for the first clinic visit; subsequently two further clinic visits will be made (i.e. three clinic visits in total after the initial "consenting" visit). Subjects will attend each of these three clinic visits in the fasted state (no food or drink except water after 9 pm the previous evening).

Subjects will visit the Wellcome Trust Clinical Research Facility, Southampton General Hospital on three occasions each between 8 and 10 am. On each occasion they will be in the fasted state. At each clinic visit weight, waist and hip circumference, and body composition (bioelectrical impedance) will be measured. Two visits will be for post-prandial study days prior to entering the chronic phase of the study. The third visit will be at the end of the chronic phase of the study, at which time a further post-prandial study day will occur. An adipose tissue biopsy will be taken from the subcutaneous abdominal area at the first and third clinic visits.

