During the post-prandial study days subjects will have a venous cannula inserted and 20 ml blood will be collected at zero time. They will then consume a standard breakfast (on one occasion with placebo capsules and on the other with fish oil capsules – this will be in random order; on the third post-prandial day only the placebo capsules will be used) and 5 ml blood will be collected at each later time point (1, 2, 3, 4 and 6 hours). Thus 45 ml blood will be collected per visit. Blood will be taken into heparin. An small adipose tissue biopsy (weighing 1 to 5 g) will be taken from the subcutaneous abdominal area at the end of the first and third clinic visits; this will be taken under local anaesthetic. At the end of each visit subjects will be offered toast and a hot drink. Subjects will receive a supply of supplements along with instructions on how to take them at the second clinic visit.

As indicated above a small adipose tissue biopsy will be taken at two of the clinic visits. The wound will be stitched and subjects will return to the Wellcome Trust Clinical Research Facility about one week later in order for the stitches to be removed.

Schedule of subject visits and activities performed at each visit

X indicates the activity will take place.

Visits 3 and 4 will be about 12 weeks apart and subjects will consume fish oil or placebo capsules daily during that period.

Activity	Visit 1	Visit 2	Visit 3	Visit 4
		(Clinic visit 1)	(Clinic visit 2)	(Clinic visit 3)
Subject in fasting state		X	X	X
Informed consent	X			
Height	X			
Weight	X	X	X	X
Waist & hip circumference	X	X	X	X
Bioelectric impedence	X	X	X	X
Blood for DNA	X			
Post-prandial study: Blood for		X	X	X
fatty acids & inflammatory				
markers				
Adipose tissue biopsy		X		X

Sample analysis

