The n-3 fatty acid supplement to be used is commercially available and is safe. Two invasive procedures will be used, adipose tissue biopsy and obtaining blood samples. The biopsy will be taken by a trained surgeon with assistance from trained nursing staff and blood samples will be taken by trained nursing staff limiting the likelihood of adverse events related to participation in the study. However if any volunteer reports any untoward medical occurrence this will be recorded on an adverse event or serious adverse event form and the PI informed immediately. If the investigator suspects that a serious adverse event is either a) related to the intervention or b) unexpected, the PI will report the event to the main REC and to a representative of the supplier of the supplement. An adverse or serious adverse event may result in the volunteer wishing to withdraw from the study or being unable to continue with the study schedule. In this case or any other instance in which a subject withdraws or is withdrawn from the study a volunteer withdrawal form will be completed. Where the reason is know to the investigator or is volunteered by the subject this will be recorded on the form. The subject will not be required to give any reason for withdrawing themselves from the study and will not be asked to do so by the investigator.

14. Stopping/Discontinuation of intervention

Completion of each subject's involvement in the study will be when the last blood sample is taken, which will be approx. 15 weeks after the subject entered the study. If there is any reason for discontinuing the intervention prior to its completion the PI will arrange for the research team to inform all volunteers immediately. The PI will also inform the sponsor and the main REC.

15. Monitoring

The project will be overseen and monitored by the Southampton University Hospitals Trust R&D Office.

Steps taken to ensure quality of research

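### Section 13 records adverse events only if a volunteer reports them and nowhere has staff ask, so events, chiefly in the roughly 12-week capsule phase, may be missed

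*Protocol*

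**What the plan says.** Protocol section 13 (Safety assessments) describes the collection of harms in one conditional sentence: "However if any volunteer reports any untoward medical occurrence this will be recorded on an adverse event or serious adverse event form". The form then leads to informing the principal investigator and, for certain serious events, to reports to the ethics committee and the supplier.

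Section 9 sets the contacts. The note to the visit table says: "Visits 3 and 4 will be about 12 weeks apart and subjects will consume fish oil or placebo capsules daily during that period". The table has rows for fasting state, consent, body measurements, blood for DNA, post-prandial blood and biopsy. It has no adverse event row at any of the four visits.

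The biopsies "will be taken from the subcutaneous abdominal area at the end of the first and third clinic visits". After each one, "subjects will return to the Wellcome Trust Clinical Research Facility about one week later in order for the stitches to be removed". No enquiry or recording task is attached to those returns.

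Section 14 closes follow-up: "Completion of each subject's involvement in the study will be when the last blood sample is taken".

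**The concern.** An event reaches the form only if the subject raises it or happens to be asked, and the protocol does not provide for asking. A subject with a minor or moderate complaint early in the capsule phase would have to telephone, or remember to mention it unprompted at a visit that may be up to about 12 weeks away. Reporting of serious events to the ethics committee depends on the same first step, because the investigator can assess only what is known.

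What is at stake is the trial's own safety record for two surgical biopsies and about 12 weeks of daily capsules. A low count could be taken as reassurance when it partly reflects who chose to speak. Section 13 opens by calling the supplement safe, and a record built this way would be a weak check on that statement.

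**Working it through.** The protocol states no figure on this point, so there is none to reproduce. The check is a timeline built from the text, followed by an illustration with assumed values.

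**Timeline, with clinic visit 1 as week 0**

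- Week 0: first biopsy, at the end of clinic visit 1 (section 9, Subject participation schedule).
- About week 1: first stitch removal.
- Week 2 or later: clinic visit 2, since section 9 (General approach) says "Each subject will undergo both meal challenges, in random order and separated by at least 2 weeks". Capsules for the chronic phase are handed out here.
- About 12 weeks after that, so week 2 + 12 = 14 or later: clinic visit 3, with the last blood sample and the second biopsy.
- About one week later, so week 15 or later: second stitch removal.

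Three things follow.

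1. The first stitch removal falls before the capsule phase and the second after it. No contact of any kind is listed between capsule supply and clinic visit 3.
2. Under section 14 involvement ends with the last blood sample, at clinic visit 3. The healing of the second biopsy wound and its stitch removal come after that sample, so sections 9 and 14 leave it unclear whether events are still collected then.
3. Section 9 places randomisation to daily capsules after both meal challenges. Events from the first biopsy therefore cannot reflect the daily capsule arm.

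**Illustration of what incomplete reporting does**

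Section 12 plans 50 + 50 = 100 subjects. Its 20 per treatment group within each weight group implies equal allocation, so 100 / 2 = 50 subjects per capsule arm. Let p be the true proportion of subjects with an event of some kind and c the share of such events that are volunteered. Both are assumptions; the documents give neither.

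- Expected recorded events in 100 subjects = 100 × p × c. With p = 5% and c = 100%, 75%, 50% and 25%, this gives 5, 3.75, 2.5 and 1.25.
- Chance of recording at least one event in an arm of 50 = 1 − (1 − p × c)^50:

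| p | c = 100% | c = 75% | c = 50% | c = 25% |
|---|---|---|---|---|
| 2% | 64% | 53% | 40% | 22% |
| 5% | 92% | 85% | 72% | 47% |
| 10% | 99.5% | 98% | 92% | 72% |

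Under these assumptions an event affecting 5% of subjects would be seen at least once in an arm with probability 92% if every case is reported, and 47% if a quarter are. The table shows the direction and how strongly the result depends on c. It does not estimate the loss in this trial.

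**The case against.** The strongest reply is that section 13 does not exclude enquiry. A subject who answers a staff question also reports an event. Where the protocol wants staff not to ask, it says so, as it does for reasons for withdrawal. The quality section under section 15 promises operating procedures covering every aspect of the study and trained staff, section 16 offers subjects the chance to discuss issues, and section 18 commits to ICH GCP. This stands in part: a reader might infer that the protocol fixes a purely spontaneous system, but the text supports only that it provides for no enquiry. The general promises do not fill the gap. None mentions asking about events, the procedures are still to be written, and the discussion in section 16 depends on the subject.

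A reader might also take the missing table row as proof that nothing is asked. The table cannot bear that weight, because it also omits capsule supply and the stitch-removal returns, both of which section 9 plans.

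The biopsy side is weaker than the capsule side. Staff see the subject about a week after each biopsy, so a wound problem is likely to be noticed even if not volunteered. That objection stands, although no recording task goes with the return.

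Finally, safety is not among the objectives or questions in section 8, and section 11 plans no safety analysis. That is correct and limits the importance of the point. It does not remove it, since section 13 does set out to collect harms. Nor can a separate analysis plan recover events that were never recorded.

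**Conclusion.** The point holds in a limited form. Recording depends on a volunteer's report, no enquiry is provided for at any visit or at stitch removal, and no contact is listed during the capsule phase. Events may be missed, chiefly in those 12 weeks.

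The size is unknown. It would be tempting to say that harms will be under-counted by some stated factor, but the documents give no event rate and no reporting share, so any such figure would only restate its assumptions. It would also be wrong to infer a bias in the trial's main results: the comparisons of inflammatory markers and fatty acids do not use adverse event data. If blinding holds, the loss should be similar in both capsule arms, which lowers absolute counts and the chance of seeing a difference between arms rather than favouring one.

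This is an inexpensive improvement to safety capture, not a flaw in the efficacy design.

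**What to change.** 1. Change section 13 so that at clinic visits 1 to 3 and at both stitch-removal returns, staff blinded to allocation ask one standard open question about any health problem since the last contact. The answer, and any biopsy-site problem seen, goes on the adverse event form.
2. Add the matching row to the visit table in section 9, with the stitch-removal returns shown.
3. Reconcile section 14 with section 9 so that event collection runs through the second stitch removal.
4. Tabulate events that start after capsule supply by capsule arm and BMI group. Tabulate earlier events, including those from the first biopsy, by BMI group only.

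The cost is one question at contacts that already take place, one or two additions to the table, and more forms. More minor events will be recorded. No contact is added within the capsule phase, so recall over about 12 weeks remains imperfect, and a subject who withdraws before clinic visit 3 would not be reached by the question there.
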